7.3 Handling Potential Intercurrent Events for the Primary and Secondary Endpoints

For all endpoints, no intercurrent event will be considered in the primary approach (treatment strategy policy), i.e., all observed data will be included in the primary analysis.

7.4 Statistical Analyses for Efficacy

The efficacy analyses will be summarized in the ITT Populations descriptively and no statistical testing will be performed in this study.

Categorical endpoints will be summarized by counts and percentages, as well as 95% confidence interval (CI) of the percentage. Continuous variables will be summarized by the number of observations, mean, standard deviation, median, minimum, maximum, and well as 95% confidence intervals (CIs) of the mean values.

The primary approach for efficacy summary is As Observed (AO).

Summary and Analysis of the Primary Endpoint

The primary endpoint will be summarized in the ITT_2_SS1 and ITT_2_SS2 Populations by counts and percentages, as well as the 95% CIs of the percentage. The AO approach will be used as the primary approach.

Sensitivity analyses of the primary endpoint will be conducted. The primary endpoint will be summarized using the Multiple Imputation (MI) to handle missing data. The details will be specified in the SAP.

Summary and Analysis of Secondary Endpoints

Summary of the secondary efficacy endpoints will be conducted using the ITT Populations with the treatment as randomized. Categorical variables will be summarized by counts and percentages, as well as 95% CIs of the percentage. The AO approach will be used.

Summary and Analysis of Additional Efficacy Endpoints

Additional endpoints, as described in the Section 3.4, will also be summarized using the AO approach. The analysis details will be provided in the SAP.

Subgroup Analysis for Efficacy

The primary endpoints, as described in Section 3.1, will be also summarized by the following subgroups using the AO approach:

- Baseline vIGA-AD (3; 4),
- Baseline EASI score (<21; ≥21), and
- Baseline EASI score (<median; ≥median).

7.5 Statistical Analyses for Safety

The safety analyses will be summarized in the double-blind period, single-blind period, and across study periods by the upadacitinib doses, based on the Safety_1_SS1 and Safety_1_SS2 Populations, Safety_2_SS1 and Safety_2_SS2 Populations, and ALL_UPA Population, respectively.

Safety will be assessed by AEs, physical examination, laboratory assessments, and vital signs. Note that missing safety data will not be imputed. Analysis details will be specified in the SAP. Adverse events will be coded using the Medical Dictionary for Regulatory Activities (MedDRA). Treatment-emergent AEs in each period are defined as those that began or worsened in severity after the first dose of study drug in each period and up to the minimum of the end date of each period and 30 days after the last dose of the study drug in each period. The number and percentage of subjects experiencing TEAEs in each period

and across study periods by the upadacitinib doses will be tabulated using the MedDRA SOC and PT, by severity, and by relationship to the study drug as assessed by the investigator. Summaries (including number of subjects, percentages and events per 100 patient-years) of SAEs, deaths, AEs leading to discontinuation, and AESI will be provided in each period and across study periods by the upadacitinib doses as well.

For laboratory and vital signs, mean change from Baseline will be summarized in each period and percentage of subject with evaluations meeting criteria for pre-defined Potentially Clinically Significant values will be summarized in each period and across study periods by the upadacitinib doses. For selected laboratory parameters, a shift table analysis will be provided in each period and across study periods by the upadacitinib doses.

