# 10.2.1 Treatment-Emergent Adverse Events

Treatment-emergent adverse events (TEAEs) are defined as follows:

- TEAEs in DB Period are defined as any adverse events that begin or worsen in severity after initiation of upadacitinib through the minimum (30 days following the last dose of upadacitinib in DB Period, or the start day of SB Period 1).
- TEAEs in SB Period are defined as any adverse events that begin or worsen in severity after initiation of upadacitinib in SB Period through 30 days following the last dose of upadacitinib in SB Period.
- TEAEs during the administration of upadacitinib are defined as any adverse events that begin or worsen in severity after initiation of upadacitinib through 30 days following the last dose of upadacitinib.

If a missing or an incomplete onset date is collected for an adverse event, the event will be assumed to be treatment-emergent unless there is other evidence that confirms that the event is not treatment-emergent (e.g., the event end date is prior to the study drug start date). Events where the onset date is the same as the study treatment start date are assumed to be treatment-emergent.

All TEAEs will be summarized overall, as well as by primary MedDRA SOC and Preferred Term. The SOCs will be presented in alphabetical order, and the PTs will be presented in alphabetical order within each SOC.

The number and percentage of subjects experiencing TEAEs and the number of events per 100 patient-years of exposure will be summarized.

TEAEs per 100 patient-years of exposure are defined as the number of TEAEs divided by the total exposure in 100 patient-years. See the calculation method below:

100 \* (Number of TEAEs) / (Total Patient Years)

where total patient years is defined as the sum of the study drug duration (defined in Section 6.0) of all subjects normalized by 365.25 and rounded to 1 decimal place.

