#### **Potentially Clinically Important Laboratory Values**

Laboratory abnormalities will be evaluated based on Potentially Clinically Important (PCI) criteria (NCI CTCAE V4.03 criteria of Grade 3 or above) in DB Period for the Safety 1, in SB Period for the Safety 2 Population and during the administration of upadacitinib for the All UPA Population. For each laboratory PCI criterion, the number and percentage of subjects who have a laboratory value meeting the criteria will be summarized. Listings will be provided to summarize subject-level laboratory data for subjects meeting PCI criteria. The PCI criteria are defined in Appendix D using CTCAE 4.03.

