#### **Liver Function Tests**

For the purpose of assessing for potential Hy's law cases, the frequencies and percentages of subjects with post-baseline liver function test values that meet the PCI criteria (defined in Appendix D) will be presented in DB Period for the Safety 1 Population, in SB Period for the Safety 2 Population and during the administration of upadacitinib for the ALL UPA Population. A listing of possible Hy's Law cases will be provided.

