#### Appendix D. Potentially Clinically Important Criteria for Safety Endpoints

The criteria for Potentially Clinically Important (PCI) laboratory findings are described in Table D-1 and Table D-2, PCI criteria for the liver function tests are described in Table D-3, and the PCI criteria for vital sign findings are described in Table D-4.

Table D-1. Criteria for Potentially Clinically Important Hematology Values

		Definition of Potentially Clinically Important
Hematology Variables	Units	Very Low
Hemoglobin	g/dL	< 8.0
Platelets count	$10^{9}/L$	< 50.0
WBC count	$10^{9}/L$	< 2.0
Neutrophils	$10^{9}/L$	< 1.0
Lymphocytes	$10^{9}/L$	< 0.5

Table D-2. Criteria for Potentially Clinically Important Chemistry Values

[figure not shown]
		Definition of Potentially Clinically Important	
Chemistry Variables	Units	Very Low	Very High
ALP	U/L		> 5.0 × ULN
SGOT/AST	U/L		$> 5.0 \times ULN$
SGPT/ALT	U/L		$> 5.0 \times ULN$
Albumin	g/L	< 20	
Glucose	mmol/L	< 2.2	> 13.9
Triglycerides	mmol/L		> 5.7
Creatinine	mcmol/L		$> 3.0 \times ULN$
Potassium	mmol/L	< 3.0 > 6.0	
Calcium	mmol/L	< 1.75	> 3.1
Sodium	mmol/L	< 130	> 155
Phosphate	mmol/L	< 0.6	
CPK	U/L		$> 5.0 \times ULN$
Total Cholesterol	mmol/L		> 10.34

**Table D-3.** Criteria for Potentially Clinically Important Liver Function Tests

		Definition of Potentially Clinically Important	
Variables	Units	Very High	
AST	U/L	$\geq$ 3 × ULN	
		$\geq$ 5 × ULN	
		$\geq 10 \times \text{ULN}$	
		$\geq$ 20 × ULN	
ALT	U/L	$\geq 3 \times ULN$	
		$\geq$ 5 × ULN	
		$\geq 10 \times \text{ULN}$	
		$\geq$ 20 × ULN	
Total Bilirubin	UMOL/L	$\geq 2 \times ULN$	
Alkaline phosphatase	U/L	$\geq$ 1.5 × ULN	
ALT (U/L) and/or AST (U/L)	ALT and/or AST $\geq$ 3 × ULN and concurrent TBL		
and concurrent TBL		$\geq 1.5 \times \text{ULN}$	
(UMOL/L)		ALT and/or AST $\geq$ 3 × ULN and concurrent TBL	
		$\geq 2 \times ULN$	

Table D-4. Criteria for Potentially Clinically Important Vital Sign Values

Vital Sign	Category	Criteria for Potential Clinically Significant Vital Signs
Systolic blood pressure	Low	Value ≤ 90 mmHg and decrease ≥ 20 mmHg from Baseline
	High	Value ≥ 160 mmHg and increase ≥ 20 mmHg from Baseline
Diastolic blood pressure	Low	Value ≤ 50 mmHg and decrease ≥ 10 mmHg from Baseline
	High	Value ≥ 100 mmHg and increase ≥ 10 mmHg from Baseline
Pulse	Low	Value ≤ 50 bpm and decrease ≥ 15 bpm from Baseline
	High	Value ≥ 120 bpm and increase ≥ 15 bpm from Baseline
Weight (adults)	High	> 7% increase from Baseline
	Low	> 7% decrease from Baseline

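### Laboratory PCI percentages count any value past an absolute limit, so abnormalities that predate a dose can be reported under it: at entry for rows with no entry limit, and again after the Week 12 dose change

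*Protocol*

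**What the plan says.** Protocol 7.5 states the summary in general terms ("percentage of subject with evaluations meeting criteria for pre-defined Potentially Clinically Significant values will be summarized in each period") and leaves the detail to the SAP. The operative rule is in SAP 10.3, under Potentially Clinically Important Laboratory Values: "the number and percentage of subjects who have a laboratory value meeting the criteria will be summarized". The limits are described there as "Potentially Clinically Important (PCI) criteria (NCI CTCAE V4.03 criteria of Grade 3 or above", and Appendix D says where they stand: "The criteria for Potentially Clinically Important (PCI) laboratory findings are described in Table D-1 and Table D-2". Every row of Tables D-1 and D-2 is a fixed value or a multiple of ULN. Liver tests have their own paragraph, a screen for possible Hy's law cases, which summarises "frequencies and percentages of subjects with post-baseline liver function test values that meet the PCI criteria" against Table D-3. That paragraph limits the count to values after Baseline but does not require worsening.

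Other safety rules in the SAP do look back. The blood pressure and pulse rows of Table D-4 need a limit and a change, for example "Value ≥ 160 mmHg and increase ≥ 20 mmHg from Baseline" and "Value ≤ 90 mmHg and decrease ≥ 20 mmHg from Baseline". A single-blind TEAE is defined through "any adverse events that begin or worsen in severity after initiation of upadacitinib in SB Period".

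The laboratory counts are made in the double-blind period (Safety 1), in the single-blind period (Safety 2), and for ALL UPA. Under SAP 4.0, ALL UPA is split into an All UPA 15 mg and an All UPA 30 mg cohort, each counting only exposure to its own dose.

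**The concern.** A percentage tabulated under a dose will be read as the frequency of severe laboratory abnormality arising on that dose. Under the stated rule it mixes two groups: subjects who crossed the limit after starting the dose, and subjects who were already past it and stayed there. A subject whose value improves on drug but remains past the limit counts as a case.

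Two things make this matter here. First, Protocol 2.2 names CPK and lipid elevations among the laboratory changes seen with upadacitinib, and these rows have no entry limit. Second, the primary objectives concern the efficacy and safety of changing dose at Week 12. If an abnormality that arose on 30 mg is counted again under 15 mg, or the reverse, the description of the dose change is blurred where the study is meant to inform. No hypothesis is tested, so these percentages are themselves the reported result.

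**Working it through.** The plan states no figure for this point, so there is none to reproduce. The check compares limits, follows one subject through the tables, and works out what one subject is worth.

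**1. Can a subject enter already past a PCI limit?** Entry limits are from Protocol 5.1, criterion 7; PCI limits are from SAP Appendix D.

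| Variable | Entry limit | PCI limit | Past PCI limit while meeting entry limit? |
|---|---|---|---|
| Hemoglobin (g/dL) | ≥ 9 | < 8.0 | No |
| Platelets (10^9/L) | ≥ 100 | < 50 | No |
| WBC (10^9/L) | ≥ 2.5 | < 2.0 | No |
| Neutrophils (10^9/L) | ≥ 1.2 | < 1.0 | No |
| Lymphocytes (10^9/L) | ≥ 0.75 | < 0.5 | No |
| AST, ALT (× ULN) | ≤ 2 | > 5 (D-2), ≥ 3 (D-3) | No |
| Creatinine | indirect, eGFR ≥ 40 | > 3 × ULN | Restrained |
| ALP, albumin, glucose, triglycerides, potassium, calcium, sodium, phosphate, CPK, total cholesterol | none | Table D-2 | Yes |
| Total bilirubin, ALP | none | Table D-3 | Yes |

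Table D-2 has 13 variables. Removing AST, ALT and creatinine leaves 13 − 3 = 10 open rows. The combined rows of Table D-3 need ALT or AST ≥ 3 × ULN, so the entry limits cover them. Criterion 7 applies in the screening period, and a Baseline draw may differ from it.

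**2. What happens at Week 12?** Reassignment depends on EASI alone (Protocol 4.1). Suppose an SS2 subject is within limits at Baseline. CPK passes 5 × ULN at Week 4 on 30 mg and is still past it at Weeks 12 and 16. The subject reaches EASI 90 and moves to 15 mg. Under the stated rule the subject is a case under UPA 30 mg (double-blind), UPA 30/15 mg (single-blind), All UPA 30 mg and All UPA 15 mg. The second and fourth entries place under the new dose an abnormality that preceded it.

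Entry limits do not block this route. For four of the five haematology rows it is restrained in another way: the dose-interruption thresholds in Protocol Table 3 for hemoglobin, neutrophils, lymphocytes and WBC equal the PCI limits. Table 3 has no row for CPK or lipids.

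**3. What does one such subject add?** Inputs are 454 subjects randomized 1:1, 8% dropout per 12 weeks, and Week 12 rates of 54% (SC1) and 65% (SC4), from Protocol 7.6.

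- Double-blind arm: 454 / 2 = 227; 100 / 227 = 0.44 points.
- SC1 (UPA 15/30): 227 × 0.92 × 0.54 = 112.8; 100 / 112.8 = 0.89 points.
- SC4 (UPA 30/15): 227 × 0.92 × 0.65 = 135.7; 100 / 135.7 = 0.74 points.

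**4. Illustration with assumed rates.** Let b be the share past a limit before the dose, q the share of those still past it later, and i new onset among the rest. Reported = b·q + i·(1 − b); new onset = i·(1 − b). None of these rates is in the documents.

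- b = 0.5%, q = 50%, i = 3%: 3.23% against 2.98%, ratio 1.08.
- b = 1%, q = 80%, i = 1%: 1.79% against 0.99%, ratio 1.81.
- b = 2%, q = 80%, i = 1%: 2.58% against 0.98%, ratio 2.63.

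**5. Do the shift tables recover the information?** SAP 10.3 shifts selected parameters from Baseline to the worst CTCAE grade but does not say which parameters are selected. Lipids are shifted to the final value on the ATP III bands of Appendix E. The top bands are ≥ 2.26 mmol/L for triglycerides and ≥ 6.21 mmol/L for total cholesterol, against PCI limits of > 5.7 and > 10.34. A crossing of the PCI limit inside the top band does not show there.

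**The case against.** The best defence is that a PCI count is a severity flag, not an incidence estimate. It sits beside change-from-Baseline summaries, shift tables by CTCAE grade in each period, and subject-level listings of everyone who meets a criterion. A reader can often trace a pre-existing case, and inclusive counting is sensible in a Hy's law screen. The double-blind arms are randomized 1:1, so entry prevalence is balanced in expectation and the absolute 15 mg versus 30 mg difference is little affected. The study is descriptive and the investigator's health judgement at entry (criterion 8) may keep prevalence low.

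Much of this stands, and it rules out several stronger readings. A reader might infer that the whole laboratory panel is affected at entry; the entry limits show otherwise for haematology and AST/ALT. A reader might infer that the percentages are inflated two-fold or more; that depends on assumed rates, and the upper ratio is an extreme corner. A reader might infer that the shift tables give no help; the selected parameters are not named, so only the lipid gap is shown. The contrast with vital signs and TEAEs is a difference of approach, not a contradiction, and Protocol 7.5 is not itself at fault because it defers to the SAP.

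The defence does not answer the open rows or the double counting after Week 12. Randomization does not protect the single-blind comparison, because the four cohorts are formed by EASI response and each carries over the laboratory history of its first dose. A listing does not change the tabulated percentage.

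**Conclusion.** The concern holds in a limited form. As written, SAP 10.3 reports under a dose some laboratory abnormalities that were present before that dose. At entry this can happen for 10 of 13 Table D-2 variables and for total bilirubin and ALP in Table D-3. After Week 12 it can happen through abnormalities that persist from the first dose into the single-blind and All UPA summaries.

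The total size cannot be derived from the documents. What can be stated is the weight of one subject: about 0.4 points in an arm of 227 and 0.9 points in a cohort of about 113, if the plan's own dropout and response assumptions hold. The ratios of 1.08 to 2.63 are illustrations only. No efficacy result and no part of the sample size depends on this. It should be corrected because the open rows include CPK and lipids and the change is cheap.

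**What to change.** In SAP 10.3, count a subject for a PCI criterion when a post-dose value meets it and one of two conditions is true: the last value before the reference dose did not meet the criterion, or the post-dose CTCAE grade is higher than the grade of that last value. A value that is only numerically more extreme should not be enough. With two scheduled post-dose draws per period (Weeks 4 and 12, or 16 and 24) and a stable abnormality whose values are exchangeable, the pre-dose value is the most extreme of three with probability 1/3. At least one later value would therefore exceed it by chance with probability 1 − 1/3 = 2/3.

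Define the reference dose for each summary:

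- Safety 1: first dose in the double-blind period.
- Safety 2: first dose in the single-blind period.
- All UPA 15 mg and All UPA 30 mg: first dose of that strength.

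Show beside each percentage the number already meeting the criterion before the reference dose, and keep the planned listing of all values meeting a criterion, so that no case disappears. In the Hy's law screen (Liver Function Tests paragraph and Table D-3) keep the inclusive count and add only the pre-dose number.

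The cost is a short SAP revision before the single database lock and some extra programming on data already collected. Study conduct does not change. The tabulated percentages become slightly smaller.

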7.6 Sample Size Determination

Assuming:

- In SS1, 54% of subjects would be EASI 90 non-responders at Week 12.
- In SS2, 65% of the subjects would be EASI 90 responders at Week 12.
- There would be no more than 8% dropouts every 12 weeks.

A total sample size of 454 subjects will result in at least 96 subjects in SC1 and SC4, to ensure the half width of 95% CI will be within 10% for EASI 90 response estimation at Week 24.

8 ETHICS

8.1 Independent Ethics Committee/Institutional Review Board (IEC/IRB)

The protocol, informed consent form(s), recruitment materials, and all subject materials will be submitted to the IEC/IRB for review and approval. Approval of both the protocol and the informed consent form(s) must be obtained before any subject is enrolled. Any amendment to the protocol will require review and approval by the IEC/IRB before the changes are implemented to the study. In addition, all changes to the consent form(s) will be IEC/IRB approved.

8.2 Ethical Conduct of the Study

The study will be conducted in accordance with the protocol, Operations Manual, International Council for Harmonisation (ICH) guidelines, applicable regulations, and guidelines governing clinical study conduct and the ethical principles that have their origin in the Declaration of Helsinki. Responsibilities of the investigator are specified in Appendix B.

For subjects in Japan only: This study will be conducted in Good Clinical Practice (GCP) compliance with Good Post-marketing Study Practice (GPSP).

8.3 Subject Confidentiality

For personal data that AbbVie controls and maintains, AbbVie has developed a robust security program to protect subject personal data focused on due diligence in design, managed change, and information security governance Information security policies govern the information security functions including identity and access management, operations, infrastructure, application, and third-party security requirements. The risk-based AbbVie Data Classification Tool dictates the level of scrutiny and control required for the relevant activities per AbbVie's information security policies taking into account the sensitivity of the data.

Before data is shared with AbbVie, the study doctor and staff will replace any information that could directly identify a subject (such as name, address, and contact information) with a generic code which AbbVie cannot link to that subject's identity in order to protect the confidentiality of the data.

AbbVie has a Data Protection Impact Assessment program to ensure and document the appropriate controls and safeguards stated above are in place for clinical trial data that it controls and maintains, and these processing activities respect privacy of clinical trial subjects. AbbVie also maintains robust security incident response policies and procedures, including requirements for the containment of any data-related incidents, the mitigation measures where needed, and notification to authorities or affected individuals where required.

AbbVie as the sponsor shall document any personal data breaches for which it is a controller and notify where required the competent national supervisory authority and/or affected participants and/or principal investigator and/or site personnel without undue delay and at the latest within 48 hours after becoming aware of such an incident. The sponsor shall create and maintain appropriate records of such an incident.

9 SOURCE DOCUMENTS AND CASE REPORT FORM COMPLETION

The investigator is responsible for ensuring the accuracy, completeness, legibility, and timeliness of the data reported. All source documents should be attributable, legible, contemporaneous, original, accurate, and complete to ensure accurate interpretation of data. Clinical site monitoring is conducted to ensure that the rights and well-being of human subjects are protected, that the reported trial data are accurate, complete, and verifiable, and that the conduct of the trial is in compliance with the currently approved protocol, ICH GCP, and applicable local regulatory requirement(s), including EU Clinical Trial Regulation 536/2014. During the COVID-19 pandemic, remote data review/verification may be employed if allowed by the local regulatory authority, IRB/IEC, and the study site.

10 DATA QUALITY ASSURANCE

AbbVie will ensure that the clinical trial is conducted with a quality management system that will define quality tolerance limits in order to ensure human subject protection and reliability of study results. Data will be generated, documented, and reported in compliance with the protocol, ICH GCP, and applicable regulatory requirements, including EU Clinical Trial Regulation 536/2014.

